Study Protocol and Statistical Analysis Plan

**Short-term Effects of Bowel Preparation on Gut Microbiome in
Patients Undergoing Endoscopic Colon Polypectomy**

China-Japan Friendship Hospital

Department of Gastroenterology

December 1, 2022

I. Background of the study

Good and adequate bowel preparation is essential for performing colonoscopy, especially for patients requiring endoscopic treatment, and the role of bowel cleansing agents (i.e., laxatives) and their safety for patients have been extensively studied [1]. A variety of laxatives are used in clinical practice, the most widely used being electrolyte-supplemented polyethylene glycol (PEG) [2], a PEG solution that rapidly passes through the gastrointestinal tract causing severe osmotic diarrhea, altering the contents of the intestinal lumen, including the microbiota [3]. In addition, other types of laxatives have been developed, such as compounded sodium picosulfate granules, which stimulate peristalsis of the intestinal mucosa and act as an osmotic laxative, increasing the water content of the intestinal lumen, and are taken with a slightly better taste than PEG.

When a large amount of laxative passes through the gut, many microorganisms are removed from the gut. This results in significant changes in the composition of the gut microbiota during the intestinal cleansing process. A number of studies have been reported on the changes in the gut microbiome produced after gut cleansing in healthy populations [4-8] to assess whether gut cleansing directly leads to dysbiosis, whether the flora is restored, and to explore the impact of this process on health and disease. However, there is no consensus on how gut cleansing affects the gut microbiome. Some studies have found an increase in the relative abundance of Bacteroidetes and Ascomycetes and a decrease in the relative abundance of Thick-walled Bacteroidetes following gut cleansing [4, 9], however, others have found that gut cleansing does not have a significant effect on the microbiome [3, 7].

Colon polyps are a common gastrointestinal tumor, and most of these lesions are histologically adenomatous, with a risk of becoming cancerous [10], showing an "adenoma-adenocarcinoma" progression, so complete resection is essential. In most patients, polyps can be completely removed at an early stage by endoscopic mucosal resection (EMR) or endoscopic submucosal dissection (ESD) to avoid progression to colon cancer [11].

There are still no studies reporting the effects of laxatives on the gut microbiome of patients with colon polyps, and in addition, most of the current studies, focusing on the effects on the gut microbiome after bowel cleansing with PEG [4, 7, 8, 12], have not explored whether other types of laxatives have different effects on the human gut microbiome. In our study, we plan to focus on different types of laxatives and explore whether they have different effects on the gut microbiome of patients with intestinal polyps after bowel cleansing, as well as to analyze whether the diameter of the colon polyps, pathological findings, and other baseline information also lead to different changes in the composition, evolution, and recovery of the gut microbiome of the patients, and to further explore the effects of microbiome changes on the patients' disease, and health.

II.Purpose of the study:

To investigate the role of different types of laxatives (compounded polyethylene glycol electrolyte dispersions and compounded sodium pico-sulfate) on the composition, evolution and recovery of the intestinal microbiome of patients with colonic polyps undergoing bowel preparation.

III.Overview of the study:

1. Study Steps:

Patients requiring e-colonoscopy and treatment for colon polyps were recruited and randomized into a polyethylene glycol group and a sodium picosulfate group. Patients in the two groups were prepared for bowel preparation with cotrimoxazole polyethylene glycol electrolyte dispersions and cotrimoxazole sodium picosulfate, respectively, while basic information about the patients was collected. Patients were left with feces before and after oral laxatives, and feces were left again 7 and 14 days after the end of intestinal cleansing, and intestinal microbiome sequencing was carried out to observe the changes in the intestinal microbiome of patients. The diameter of colonic polyps was recorded during the patients' operation, and the pathological results of colonic polyps were followed up after the operation.

2. Study population:

Patients who need to undergo electronic colonoscopy and treatment due to colon polyps.

3. Inclusion criteria:

- 1) All colon polyps diagnosed by electronic colonoscopy.
- 2) Age above 18 years old.
- 3) Patients sign an informed consent form, agree to cooperate with the study of this project, and collect fecal specimens on time to receive follow-up visits.

4. Exclusion criteria:

- 1) Patients who received antibiotics, PPIs 2 weeks before the study.
- 2) Patients who consumed probiotics or herbs 2 weeks prior to the study.
- 3) Had a colonoscopy or used diarrhea-inducing drugs or gastrointestinal stimulants 1 week prior to the study.
- 4) Gastrointestinal surgery and gastrointestinal endoscopic procedures in the 1 month prior to the study.
- 5) Bacterial or parasitic intestinal infections in the 1 month prior to the study.
- 6) Patients on long-term low-calorie diets, vegan diets, gluten-free diets and other "special" diets.
- 7) Pregnant/nursing patients.
- 8) Patients with a history of hypersensitivity to relevant medications.
- 9) Patients with contraindications to sodium picosulfate: renal insufficiency, renal transplant recipients, congestive heart failure, symptomatic ischemic heart disease within the last 6 months, cirrhosis of the liver, patients on hemodialysis or peritoneal dialysis, patients taking certain medications - renin-angiotensin blockers, diuretics, non-steroidal anti-inflammatory drugs (NSAIDs), and patients taking medications known to trigger the syndrome of inappropriate secretion of antidiuretic hormone. patients taking medications known to induce the syndrome of inappropriate antidiuretic hormone secretion (tricyclic antidepressants, selective 5-hydroxytryptamine reuptake inhibitors, multiple antipsychotics, and carbamazepine).
- 10) Patients with contraindications to colonoscopy, such as severe hypertension, anemia, coronary artery disease, cardiopulmonary insufficiency, etc..
- 11) Patients with contraindications to drug-induced diarrhea, such as intestinal obstruction, electrolyte disorders, or severe renal insufficiency.
- 12) Any other reason the investigator considers inappropriate for enrollment.

IV Statistical analysis:

Calculation of multiple Alpha diversity indices (richness, Chao1, Shannon, etc.) based on the (Z)OTU abundance table was performed using the USEARCH alpha_div subcommand (version 11.2.64). USEARCH beta_div was used to calculate the beta diversity distance matrices between samples, including weighted_unifrac, unweighted_unifrac and bray_curtis. Based on the three beta diversity distance matrices, PCoA analysis was performed and plotted using the R software, and based on the homogenization of OTUs. abundance table, PCA analysis was performed and plotted at different taxonomic levels using the gmodels package of R software, NMDS analysis was performed and plotted based on the three beta diversity distance matrices using the NMDS package of R software, and the three beta diversity distance matrices computed based on the homogenized OTU abundance table were analyzed and plotted using the Vegan package of R software (Version 2.4.2). Anosim analysis and mapping. Differential species composition was identified using DESeq2 (Version 1.26.0). Functional information in the samples was mined based on 16S sequences, mainly using the KEGG database of known bacteria and their functional annotation information for prediction. The investigators used the BLAST method to compare the (Z)OUT representative sequences with the SILVA_123_SSURef_Nr99 database to complete the sequence classification of the OTUs, and then used the Tax4Fun (version 0.3.1) package for R to obtain detailed abundance information of the KOs, and used the high level KEGG annotations of the metabolic pathways, enzymes, reactions, etc., which were associated with the KOs. information, and finally statistically analyzed and presented.

The routine data were processed using SPSS 25.0 statistical software, and the measurement information was tested by Kolmogorov-Smirnov test for conformity to normal distribution; the measurement information conforming to normal distribution was expressed as mean \pm standard deviation, and the comparison between groups was performed by independent samples t-test; the measurement information not conforming to normal distribution was expressed as median and 25%-75% quartiles, and the comparison between groups was performed by Mann-Whitney U test; count data were described as the number of cases and percentages, and comparisons between groups were made using the χ^2 test, with successive corrected chi-square values when the theoretical frequency of any cell was $1 < E < 5$ and Fisher's exact test when the theoretical frequency of any cell was ≤ 1 ; hierarchical data were used with the Mann-Whitney U test;

V. Research-related ethics

1. Ethics Committee Review

The protocol and written informed consent and information directly related to the subjects must be submitted to the Ethics Committee, and the study can be formally conducted only after obtaining written approval from the Ethics Committee. The investigator must submit an annual report of the study to the Ethics Committee at least once a year. The investigator must notify the Ethics Committee in writing upon termination and/or completion of the study; the investigator must report to the Ethics Committee in a timely manner all changes occurring in the conduct of the study (e.g., revisions to the protocol and/or informed consent form) and must not implement these changes without first obtaining the approval of the Ethics Committee unless the changes are made in order to eliminate a clear and immediate risk to

the subjects. The Ethics Committee will be notified when this occurs.

2. Informed Consent

The investigator must provide the subject or his/her legal representative with a readily understandable and Ethics Committee-approved informed consent form and allow the subject or his/her legal representative sufficient time to consider the study, and the subject will not be enrolled until a signed written informed consent has been obtained from the subject. Subjects will be provided with all updated versions of the Informed Consent Form, as well as written information, for the duration of their participation. The informed consent form is retained for review as an important document of the clinical trial.

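### Does the word cotrimoxazole before both bowel preparations in the Study Steps leave the randomised treatments in doubt?

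*Combined protocol and SAP*

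**What the plan says.** Section II (Purpose) describes the study as a comparison of different types of laxatives and names them as "compounded polyethylene glycol electrolyte dispersions and compounded sodium pico-sulfate". Section I (Background) introduces the second product among other laxatives, "such as compounded sodium picosulfate granules", and calls the first an electrolyte-supplemented polyethylene glycol.

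Section III.1 (Study Steps) says patients are "randomized into a polyethylene glycol group and a sodium picosulfate group". The next sentence says the two groups were "prepared for bowel preparation with cotrimoxazole polyethylene glycol electrolyte dispersions and cotrimoxazole sodium picosulfate". The sampling sentence after it reads "Patients were left with feces before and after oral laxatives", with further samples 7 and 14 days after cleansing.

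Section III.4 (Exclusion criteria) has three relevant entries: criterion 1, "Patients who received antibiotics, PPIs 2 weeks before the study"; criterion 8, "Patients with a history of hypersensitivity to relevant medications", which lists no products; and criterion 9, "Patients with contraindications to sodium picosulfate", followed by a list of conditions and drugs.

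**The concern.** The disputed word stands in the only sentence of the document that gives each randomised group its product, so it changes the literal description of the intervention in both arms. The documents do not say what cotrimoxazole is. Taken as the antibiotic of that name, it would sit oddly in a study that excludes recent antibiotic users so that the microbiome can be read cleanly.

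If an antibiotic really were part of both preparations, the contrast between arms would still be polyethylene glycol against sodium picosulfate, because the addition is common to both. The change within each arm from the first sample to the samples after cleansing and at days 7 and 14 would then mix laxative and antibiotic effects, and the study's questions about composition and recovery rest on that change.

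A smaller worry concerns screening. Criterion 8 turns on products that it does not list, and the two sections that name both products in full disagree.

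**Working it through.** No arithmetic applies beyond counting words. The check sets the places that name the products side by side.

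| Place | Polyethylene glycol product | Picosulfate product |
|---|---|---|
| I. Background | electrolyte-supplemented | compounded, granules |
| II. Purpose | compounded, electrolyte dispersions | compounded |
| III.1, group names | no qualifier | no qualifier |
| III.1, preparation sentence | cotrimoxazole, electrolyte dispersions | cotrimoxazole |
| III.4, criterion 9 | not named | no qualifier |

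1. **Counts.** Cotrimoxazole: 2, both in the preparation sentence. Compounded: 1 (Background) + 2 (Purpose) = 3.

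2. **Position.** Apart from a hyphen in picosulfate, the Purpose and the preparation sentence name the two products in the same words and the same order, except that cotrimoxazole stands where the Purpose has compounded, both times. One word replaced throughout a parallel phrase is what a translation slip looks like. An added drug would be expected to bring an ingredient, a reason for its use or a safety provision, and the document has none of these.

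3. **Group names.** The sentence just before, "randomized into a polyethylene glycol group and a sodium picosulfate group", defines the arms without the word.

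4. **Sampling.** "Patients were left with feces before and after oral laxatives" times the stool samples around laxatives only.

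5. **Exclusion criteria.** There are 12. None names cotrimoxazole. Antibiotics appear once, in criterion 1. Criteria 9, 10 and 11 deal with contraindications to sodium picosulfate, to colonoscopy and to drug-induced diarrhea, and none deals with cotrimoxazole.

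6. **Criterion 8.** The group names give both laxatives and criterion 9 repeats one of them, so a screener can read the criterion without the disputed sentence. Suppose a screener nonetheless also excluded patients hypersensitive to cotrimoxazole. Those exclusions would come at enrolment, before allocation if screening precedes randomisation as the order of the Study Steps implies, and so could not unbalance the arms.

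7. **Analysis.** Section IV covers diversity indices, ordination, differential abundance, predicted function and routine comparisons between groups. It contains no term for a product name or for cotrimoxazole. Samples, estimates and analyses affected: 0.

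**The case for a change.** The strongest opposing case is that the identity of the intervention is the last thing a protocol should leave to inference. The word is a correctly spelled drug name used twice in current text, in the sentence that matters most for naming. It is not a redaction, and a PDF-reading fault is an unlikely cause. A probable slip makes correction easy, and that is no reason to leave it. With one set of names, criterion 8 could be read without looking elsewhere.

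The factual part of this stands: the sections disagree, and the sponsor should reconcile them. The practical part is weak. The route through criterion 8 fails because the group names already identify both laxatives. Bringing the Study Steps into line with the Purpose and the Background would not give one name throughout either, because those two sections describe the polyethylene glycol product differently. Other wording slips, such as the garbled sampling sentence and a transposed (Z)OTU in Section IV, likewise leave the meaning recoverable.

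The points from the exclusion list carry limited weight. Criterion 1 concerns use in the 2 weeks before the study and does not settle what a product is called. The group names and the parallel phrasing are the better evidence.

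**Conclusion.** The discrepancy is real and clerical: 2 uses of one word in one sentence, set against group names, a stated purpose and a sampling schedule that all describe a comparison of two laxatives. Correcting it would alter nothing that the trial does, estimates or concludes, so no change to the plan follows. Reconciling the product names across the Background, the Purpose and the Study Steps is housekeeping that can go with any other revision; Section V.1 requires Ethics Committee approval before a revision is implemented.

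The conclusion assumes that the word is a wording error, which the context supports but the documents do not state. If the sponsor reported that a further drug was in fact part of the preparations, the within-arm changes would have to be interpreted afresh and this judgement would no longer hold.

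### No stated comparison of the two laxatives on alpha diversity uses the pre-laxative stool sample, so precision may be lost

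*Combined protocol and SAP*

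**What the plan says.** Section II sets out to compare two laxatives on the "composition, evolution and recovery of the intestinal microbiome of patients with colonic polyps undergoing bowel preparation". Section III.1 randomises patients to polyethylene glycol or sodium picosulfate and fixes four sampling times: "Patients were left with feces before and after oral laxatives, and feces were left again 7 and 14 days after the end" of cleansing. It gives the reason for sequencing: "intestinal microbiome sequencing was carried out to observe the changes in the intestinal microbiome of patients".

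Section IV takes alpha diversity only as far as computing the indices: "Calculation of multiple Alpha diversity indices (richness, Chao1, Shannon, etc.) based on the (Z)OTU abundance table was performed" in USEARCH. No contrast, visit, baseline term or model follows.

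The last paragraph of Section IV opens with "The routine data were processed using SPSS 25.0 statistical software". For normally distributed measurements, "the comparison between groups was performed by independent samples t-test"; for the others, "the comparison between groups was performed by Mann-Whitney U test". Section IV names no ANCOVA, change score, paired test, repeated-measures analysis or mixed model.

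**The concern.** Recovery is a return towards a patient's own starting state, so the pre-laxative sample is central to the stated aim. Yet no stated analysis brings it into the comparison of the laxatives on alpha diversity. If the arms are compared visit by visit with the tests in the last paragraph of Section IV, stable differences in diversity between patients stay in the error term, although the sample that could remove part of them has already been collected.

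What is at stake is the width of the confidence interval for the difference between laxatives, and the chance of detecting a difference of a given size. The quantitative claim covers continuous, roughly normal alpha indices only.

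**Working it through.** **What the documents supply.** Two randomised arms, one pre-laxative sample and three later samples per patient (Section III.1). They state no sample size, allocation ratio, significance level, power, effect size, SD or correlation, so there is no planned figure to reproduce.

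**What is assumed.** Equal arms of n = 20 or 30; two-sided 5% level; a true difference of 0.7 follow-up SD; rho = 0.1, 0.3, 0.5 or 0.7.

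**Step 1: variance.** Relative to the unadjusted comparison, ANCOVA multiplies the variance of the arm difference by 1 - rho^2. Allowing for estimation of the slope, the factor is (1 - rho^2)(1 + 1/(2n - 4)). At n = 20 the second term is 1 + 1/36 = 1.028. At rho 0.5 this gives 0.75 x 1.028 = 0.77.

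**Step 2: break-even.** ANCOVA gains when (1 - rho^2)(1 + 1/(2n - 4)) < 1, that is, when rho > sqrt(1 - 1/(1 + 1/(2n - 4))). This is 0.164 at n = 20 and 0.132 at n = 30.

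**Step 3: interval width and power.** The 95% CI half-width is t(0.975, df) x sqrt((2/n) x factor), in follow-up SD. Power comes from the noncentral t distribution. The df are 2n - 2 unadjusted and 2n - 3 for ANCOVA. Unadjusted at n = 20, the half-width is 2.024 x sqrt(0.1) = 0.64.

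| | Unadjusted | rho 0.1 | rho 0.3 | rho 0.5 | rho 0.7 |
|---|---|---|---|---|---|
| 1 - rho^2 | 1 | 0.99 | 0.91 | 0.75 | 0.51 |
| Factor with slope cost, n = 20 | 1 | 1.02 | 0.94 | 0.77 | 0.52 |
| CI half-width (SD), n = 20 | 0.64 | 0.65 | 0.62 | 0.56 | 0.46 |
| Power, n = 20 | 58% | 57% | 61% | 69% | 85% |
| Power, n = 30 | 76% | 76% | 79% | 86% | 96% |

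**Step 4: would a change score do instead?** Let k be the follow-up SD divided by the baseline SD. The variance factor is then 1 + 1/k^2 - 2 rho/k, with break-even at rho = 1/(2k).

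| k | rho 0.1 | rho 0.3 | rho 0.5 | rho 0.7 | Break-even rho |
|---|---|---|---|---|---|
| 0.7 | 2.76 | 2.18 | 1.61 | 1.04 | 0.71 |
| 1 | 1.80 | 1.40 | 1.00 | 0.60 | 0.50 |
| 1.5 | 1.31 | 1.04 | 0.78 | 0.51 | 0.33 |

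With equal SDs and rho 0.3, power at n = 20 falls to 45%, against 58% unadjusted and 61% by ANCOVA. The ANCOVA factor does not depend on k.

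**The case against.** The strongest reply is that the plan has made no choice to criticise. A reader might infer that Section IV commits the trial to unadjusted tests of alpha diversity. It does not: those tests are introduced for routine data, and the text never says whether the microbiome indices are included. Nor does silence show that the baseline will be ignored. The aim of observing changes suggests that within-patient change was in mind, and the t-test or Mann-Whitney test could be run on change scores. All of this stands, and it makes the loss conditional. It does not supply the missing analysis, and a change score is an unreliable substitute (Step 4).

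A reader might also infer bias or an inflated false-positive rate. The documents do not support that: arms are randomised, so an unadjusted comparison after the laxative remains valid.

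The size is open too. Every numerical input is assumed, the study describes itself as exploring, and no primary outcome is named, so the power figures illustrate relative efficiency and are not a forecast for this trial. In a very small trial the cost at low correlation is a little larger: at 10 per arm the break-even is near rho 0.24, and power at rho 0.1 is 30% against 32% unadjusted.

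Two practical objections also have some force. Linear ANCOVA does not suit every index, and Section IV itself provides for non-normal measurements; the fix has to cover that. And it may be late for a change: Section IV is in the past tense and one reference is dated 2023, although the document is dated December 1, 2022. Translation or later editing could explain both, so neither shows that data had been seen.

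**Conclusion.** The point holds as an omission with a conditional cost. Section IV states no between-laxative analysis of the alpha indices that uses the pre-laxative sample. If unadjusted single-visit tests are used, the comparison is valid but may be less precise than the collected data allow.

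The size depends on rho. At 20 per arm, adjustment costs about one percentage point of power at rho 0.1 and adds about 11 points at 0.5 (69 - 58) and 27 at 0.7 (85 - 58), for an assumed 0.7 SD difference. The downside is slight and the possible gain large, which is enough to recommend the change. The documents cannot show which end of the range applies, and they do not support a statement that this trial is underpowered or that its results would be wrong. Confidence is medium because rho is unknown and washout may lower it, particularly in the first sample after the laxative.

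**What to change.** Add to Section IV, for each named alpha index (richness, Chao1, Shannon and any other that will be reported):

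- Compare the arms at the post-laxative, day 7 and day 14 visits by ANCOVA, with the patient's own pre-laxative value as covariate. Alternatively, use one mixed model with a patient random effect and arm, visit, arm-by-visit and baseline-by-visit terms.
- Report the baseline-adjusted arm difference with its 95% CI at each visit.
- For clearly non-normal indices, use a log transformation or a rank-based ANCOVA.
- Do not substitute a plain change score. With equal SDs it loses precision when rho is below 0.5, and that threshold moves if the spread changes after washout.
- State whether the routine-data tests apply to any microbiome index.

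The cost is a little more analysis work and a slight loss of precision if the correlation is very low. No extra samples or sequencing are needed. Section V.1 requires Ethics Committee approval before a protocol revision is implemented. The revision should be settled before arm-level microbiome data are seen; Section VII expects completion by September 30, 2023.

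### ANOSIM, the only test named on the beta-diversity distances, can reject because of spread alone or go blind, and the plan has no dispersion test to separate this from a shift in composition

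*Combined protocol and SAP*

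**What the plan says.** Section IV (Statistical analysis) computes distances between samples, "including weighted_unifrac, unweighted_unifrac and bray_curtis". It then lists displays with no test attached: "PCoA analysis was performed and plotted using the R software", followed by PCA and NMDS. The vegan package is applied to "the three beta diversity distance matrices computed based on the homogenized OTU abundance table", and the method given is "Anosim analysis and mapping".

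The section does not state the grouping factor, the number of permutations, the significance level, how repeated samples are handled, or how a significant ANOSIM will be read. No PERMANOVA and no test of multivariate dispersion appears anywhere. A second inferential route to composition is given: "Differential species composition was identified using DESeq2 (Version 1.26.0". It does not use the distance matrices. The rest of the section covers routine data with univariate tests.

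The design has two arms, with patients "randomized into a polyethylene glycol group and a sodium picosulfate group". Each patient is sampled before and after the laxative, and "feces were left again 7 and 14 days after the end of intestinal cleansing". No allocation ratio or sample size is stated. Section II gives the aim as the effect of laxative type "on the composition, evolution and recovery of the intestinal microbiome of patients with colonic polyps undergoing bowel preparation".

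**The concern.** ANOSIM asks whether pairs from different groups are, by rank, further apart than pairs from the same group. Two different things can produce that pattern: the groups have different centres, or one group is more scattered. The first is a shift in composition. The second is a change in patient-to-patient variability.

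A strong lavage followed by recovery is a setting in which scatter may change between time points, and perhaps between laxatives. If it does, a significant ANOSIM does not show which of the two happened, and a non-significant one may hide a real shift. Composition is the first of the three stated targets, and ANOSIM is the only whole-community test planned for it.

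**Working it through.** **Inputs.** The plan gives no sample size, significance level or effect size, so there is no figure of its own to reproduce. Assumed: nominal 5%, Gaussian data with identical centres, Euclidean distance, 10 dimensions unless stated, SD 1 in one group and *s* in the other. The 10-dimension runs used 99 or 199 permutations and about 300 replicates per setting. At a rate of 35%, the simulation standard error is √(0.35 × 0.65 / 300) = 2.8 percentage points.

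**Statistic.** R = (mean rank between − mean rank within) / (M/2), with M = N(N − 1)/2 pairs.

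**Why spread and group size matter.** Expected squared distances in *p* dimensions are 2p within the tight group, 2ps² within the variable group and p(1 + s²) between. For p = 10 and s = 1.5 these are 20, 45 and 32.5.

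- 30 v 30: each group supplies 435 of the 870 within-group pairs. The within-group mean is (20 + 45)/2 = 32.5, equal to the between-group mean. PERMANOVA works on squared distances and keeps this balance. Ranks do not: mean R in the runs was about 0.08, enough to reject.
- 40 v 20, smaller group variable: within-group pairs are 780 tight and 190 variable. The mean is (780 × 20 + 190 × 45)/970 = 24.9, below 32.5, so R is pushed up.
- 20 v 40, larger group variable: (780 × 45 + 190 × 20)/970 = 40.1, above 32.5, so R is pushed below zero. A real shift must first overcome that.

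**Independent samples, rejection rates (range over repeated runs)**

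| Sizes | SD ratio | More variable group | ANOSIM | PERMANOVA |
|---|---|---|---|---|
| 30 v 30 | 1.0 | neither | 6% | 6% |
| 30 v 30 | 1.25 | one | 32-39% | 3-7% |
| 30 v 30 | 1.5 | one | 96-98.5% | 5-6% |
| 31 v 29 | 1.25 | smaller | 60% | – |
| 29 v 31 | 1.25 | larger | 12% | – |
| 40 v 20 | 1.25 | smaller | 96-97% | 9-11% |
| 40 v 20 | 1.5 | smaller | – | 15-20% |
| 20 v 40 | 1.25 | larger | 0% | 2% |

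**Same patients before and after (30 pairs, unrestricted permutation)**

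- No difference in spread: ANOSIM rejects 0-1%, so it is conservative.
- SD ratio 1.25: 14%, 6% and 2% at within-patient correlations 0.3, 0.5 and 0.7. A separate set of runs gave 19%, 2% and 1%.
- SD ratio 1.5: 89-96% in one set of runs and 82-94% in the other.

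**Same patients, permutation restricted within patient, spread-only differences.** ANOSIM rejects 50-100% and PERMANOVA 3.5-6%. Restricting the permutations therefore does not cure ANOSIM.

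**Dimension.** Inflation is not universal. In 100 dimensions at SD ratio 2, ANOSIM rejected 1%, 5% and 34% at 10, 20 and 40 per group. In 2 dimensions at 20 v 20 it rejected 27% and 77% at ratios 1.5 and 2.

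**Effect of a dispersion test.** It flagged the spread difference in 93-100% of replicates. ANOSIM significance without a dispersion flag then fell to 0-5%.

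**The case against.** Four objections carry weight.

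- **Pairing.** The most natural setting for a change in spread is before versus after in the same patients. There, with unrestricted permutation, most of the inflation at ratio 1.25 disappears. This stands and limits the size of the point. It does not remove it, because the rate stays near 90% at ratio 1.5.
- **Effect size.** ANOSIM reports R beside p. With equal groups mean R was only about 0.03 at ratio 1.25 and 0.08 at 1.5, and a careful reader would see little separation. The ordination plots may also show a difference in spread. Neither is a formal check, and the plan has no rule for using them.
- **Spread is assumed.** The documents give neither the direction nor the size of any change in spread, least of all between the randomised arms. The simulations show what could happen, not what will.
- **PERMANOVA is not immune.** It reaches 15-20% at 40 v 20 and ratio 1.5 when the smaller group is the more variable. Swapping one test for the other is therefore not enough, and the dispersion test is the essential part of the remedy.

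A reader might also infer more than the documents support. ANOSIM is not the plan's only test of composition, since DESeq2 tests taxa one at a time. A difference in spread does not always make ANOSIM reject: the rate was 0% when the larger of two very unequal groups was the more variable. Nor does the plan say that a significant ANOSIM will be reported as a change in composition. It gives no reading rule at all. The 40 v 20 figures show the mechanism only, because nothing in the plan suggests that imbalance.

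**Conclusion.** The point holds in conditional form. On the beta-diversity matrices the plan relies on one test that mixes spread with location, and it has nothing to tell them apart. With 30 v 30 independent samples in 10 dimensions, spread alone gives about 35% rejection at SD ratio 1.25 and 96-98% at 1.5, against a nominal 5%. With paired before/after samples and unrestricted permutation, the figures are about 2-14% and near 90%. The same test is conservative for paired samples with equal spread. It becomes blind when the larger group is clearly the more variable; the 0% there is a rejection rate without a shift, and loss of power was inferred from the negative R, not simulated.

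Sample sizes, significance level, dimension, correlations and SD ratios are all assumptions. The mechanism does not depend on these exact values, but the size does.

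**What to change.** Amend section IV as follows.

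1. Report a test of homogeneity of multivariate dispersion beside every group comparison on the three matrices.
2. Make PERMANOVA the inferential test on the same matrices. Restrict permutations within patient for time comparisons, and permute whole patients for the arm comparison.
3. State that a result is called a composition shift only after the two tests are read together, with particular care where group sizes differ.
4. Keep ANOSIM, if wanted, as a descriptive plot.

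These methods are available in vegan, which the plan already names. The cost is SAP wording, a few lines of R and a little more analysis. The downside is that some ANOSIM-significant results will no longer be claimed as composition shifts.
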